### **Group Treatment Modalities**

**(1) Treatment Group = STEP-Home.** This group will meet for ~1.5 - 2 hours a week for 12 weeks. The core skills of Emotional Regulation (ER) (45-minutes) and Problem Solving (PS) (45-minutes) are introduced and then integrated throughout all Veteran-specific content modules for practice and repetition for 12 weeks. Attention Training (AT) augments PS and ER core skills and is interspersed throughout group and individual sessions. Additional 30-minute individual skill building and goal setting sessions (see STEP-Home Manual and [1] for additional information) may occur approximately 4 - 6 times over the 12 weeks (based on individual Veteran needs). All Veterans will be offered individual skill building sessions. We have observed in past STEP-Home groups that not all Veterans chose to take advantage of these sessions, but they will be offered to all of the participants. Advisors support practice of PS/ER/AT strategies.

**Core Skills:**

Problem-Solving (PS): Participants receive 12 45-minute sessions of group PS using the five-step approach to PS [56;57]. An acronym (SWAPS) has been developed based on these steps to help participants remember them: Step 1: Stop! Is there a problem? Step 2: What is the problem? Step 3: Alternatives and options Step 4: Pick and Plan Step 5: Satisfied? Veterans learn the approach using a variety of Veteran-centric examples with repetition in multiple contexts allowing the process to become habitual or rote.

Emotional Regulation (ER): Participants receive 12 45-minute sessions of group ER drawing on the principles outlined by D'Zurilla et al. [58; 59] and their application to TBI by Rath [60]. Cognitive behavioral techniques adapted to the unique cognitive needs of Veterans will be used [60, 61]. Emotions inevitably affect (positively or negatively) PS; therefore, ER is crucial to effective PS and anger/impulse control. To maximize generalization, ER will be contextualized by focusing on real-life Veteran problems. Group members are encouraged to share a problem that they have experienced and apply ER to that problem. As Veterans become more aware and adept at this process, they are taught to identify new, healthy alternative behaviors.

Attention Training (AT): AT is based on Attention Process Training (APT-II) [62] and Sohlberg et al.'s [63] model of attention. Attention is made up of two categories: simple attention (focused and sustained attention) and complex attention (selective, alternating, and divided attention). We use these principles to guide remediation of attentional impairments through the application of individually tailored feedback including compensatory and generalization strategies. Group discussions are focused on how individual attentional difficulties can be related to symptoms of PTSD, TBI, and/or other conditions.

**Veteran-specific Content (see [1] and STEP-Home Manual for more information):** Veteran-specific content is introduced and used for PS/ER/AT skills training throughout the 12-week workshop (Figure 4). The skills training that Veterans receive is fully contextualized into the content areas. We have found that Veterans typically demonstrate difficulty adjusting from military to civilian contexts based on fundamental differences in the structure of these contexts. Similar to Battlemind training [45], we use Veteran-specific content areas to demonstrate that the habitual skills needed to survive in combat may cause problems if not adapted to the civilian world. Psychoeducation in the various content areas is provided and group leaders elicit examples from Veteran participants in the content areas to practice PS/ER/AT in group. Content domains are described in

detail in the STEP-Home Manual and include: Vocational, Community Reintegration, Psychoeducation & Destigmatization (gateway to VA care), Substance Misuse, Anger Management, Veteran-to-Veteran Support, Family/Support System Involvement.

**(2) Comparison Group = PCGT.** A nonspecific comparison design [64] was selected to allow greater certainty that STEP-Home treatment effectiveness is due to specific aspects of the key ingredients of the experimental therapy (STEP-Home) and not merely to nonspecific therapeutic factors. PCGT was initially developed by Schnurr et al. [65] to include all elements of effective PTSD treatment that are not specifically trauma-focused. PCGT is a credible and clinically acceptable treatment often used as a control condition in PTSD trials with notably low drop out rates [65-67]. It is a nonspecific and supportive intervention to control for the nonspecific benefits of the group experience (e.g., therapist contact, instillation of hope, expectation of improvement). PCGT is fully manualized for group delivery and can be easily matched to STEP-Home as an active control arm (e.g., [65-67]). It will focus on identifying and discussing current life stressors that contribute to reintegration difficulties, psychoeducation, and promotion of wellness and physical health. Similar to the STEP-Home group, PCGT will contain homework assignments, involving monitoring diaries of stressful situations and when symptoms cause impairment in social and occupational functioning, and will also meet for ~1.5 - 2 hours a week for 12 weeks. Staff members will also offer to meet individually with Veterans enrolled in PCGT before or after group approximately 4 - 6 times over the 12 weeks. PCGT and individual sessions will not include the components that form the key ingredients or core skills of STEP-Home: CBT-based active PS, ER, or AT. Rather, PCGT employs Yalom's [68, 69] model of group therapy with a "here-and-now" focus and emphasizes the process of interpersonal learning, group cohesion, and group support. Although focus of group discussions will often be on group members' current problems, active CBT-based directive PS techniques used in STEP-Home will not be employed in the PCGT control condition. Content for group discussions will mimic STEP-Home topics including: Vocational, Community Reintegration, Psychoeducation & Destigmatization (gateway to VA care), Substance Misuse, Anger Management, Veteran-to-Veteran Support, and Family/Support System Involvement.

## **Outcome Measures**

All measures used (except those developed for STEP-Home during the feasibility study) are commercially available, have evidence of psychometric soundness or responsiveness to the interventions proposed, and have been used in previous intervention studies of populations with PTSD and TBI. Assessments do not require blinding because all outcomes are self-report. The time points at which the different outcome measures will be administered are shown in the Table below that follows the listing of outcome measures.

### **(1) Primary Outcome Measures**

The primary outcome measures may include the following assessments:

- Military to Civilian Questionnaire (M2C-Q): A 16-item measure of post-deployment community reintegration in post-9/11 Veterans that assesses six domains (interpersonal relationships, productivity at work, school or home, community participation, self-care, leisure, and perceived meaning of life).
- Post-Deployment Readjustment Inventory (PDRI): A 36-item measure of readjustment in post-9/11 Veterans with six subscales (career challenges, social difficulties, intimate relationship problems, health concerns, concerns about deployment, and PTSD symptoms).
- State-Trait Anger Expression Inventory (STAXI-2): A 57-item widely used measure to assess state anger, trait anger, and anger expression with three subscales (trait anger, anger expression, and anger control).

### **Core Skills Measures**

The core skills measures may include the following assessments:

- Problem Solving Inventory (PSI): Measure of PS Confidence, Approach-Avoidance Style and Personal Control.
- Difficulties in Emotion Regulation Scale (DERS): Measure to assess multiple aspects of emotion dysregulation
- Attention-Related Cognitive Errors Scale (ARCES): Measure of everyday performance failures arising from brief failures of sustained attention.

## **(2) Secondary Outcome Measures**

The secondary outcome measures may include the following assessments:

### *Mental Health*

- PTSD Checklist for DSM-5 (PCL-5): A 20-item measure of PTSD updated for DSM-5.
- Depression Anxiety and Stress Scale (DASS-21): A 21-item measure of current depression, anxiety, and stress.
- Neurobehavioral Symptoms Inventory (NSI): A 22-item measure of current post-concussive symptoms.

### *Functional/Vocational*

- World Health Organization Disability Assessment Schedule-2.0 (WHODAS-2.0): Measures functional states in six domains (understanding and communicating, getting around, self care, getting along with people, life activities (work/school), and participation in society).
- Satisfaction with Life Scale (SWLS): A 5-item measure of satisfaction with life.
- Treatment/Activities Survey: Assesses engagement in treatment, school, work, and life activities.
- Barriers to Employment Success Inventory (BESI): A measure of obstacles to employment in five areas (Personal/Financial, Emotional/Physical, Career Decision-Making and Planning, Job-Seeking Knowledge, and Training/Educaiton).
- Average # hours worked: Number of hours/month in the month before STEP-Home and in each month of the intervention, WLC, and post-treatment monitoring.

### *Cognitive*

- Frontal Systems Behavior Scale (FrSBe): Measures apathy, disinhibition, and executive dysfunction.

### *Baseline Characteristics (captured via self-report measures and/or CPRS chart review)*

- Demographics
- Deployment data
- Active problems/diagnoses
- Medication list
- Health utilization data
- WTAR

## **(3) Treatment Adherence and Program Satisfaction Measures**

### *Feasibility/Adherence*

- Supervisor Adherence: Supervisor Assessment of Therapist Adherence to Content
- Therapist Adherence: Therapist Self-Assessment of Adherence to Content
- Fidelity to Content: Participants rate fidelity to content
- Program Satisfaction: Participants rate interest, pace of delivery, and relevance of workshop goals with global and specific satisfaction ratings
- Participant Skills Self-Rating: Knowledge of core skills/key therapeutic ingredients
- Connectedness to VA services measure: Participants rate perceptions of engagement to treatment and VA

Therapist adherence to each intervention (STEP-Home and PCGT) will be rated by a supervisor. Therapists will be informed of these adherence ratings during training. Treatment adherence is an essential element of RCT design and these ratings will be required for all therapists.

Domain	Screening	T1 Baseline 0 weeks	T2 Skills check 4 weeks	T3 Skills check 8 weeks	T4 Post- Intervention 12 weeks	T5 Follow up 24 weeks
Baseline Characteristics						
Demographics	X					
Deployment data	X					
Active problems/diagnoses	X	X			X	X
Medication list	X	X			X	X
Health utilization data	X	X			X	X
WTAR	X					
Primary Outcomes						
M2CQ	X	X			X	X
PDRI	X	X			X	X
STAXI-2	X	X			X	X
Core Skills/Key Ingredients						
PSI		X	X	X	X	X
DERS		X	X	X	X	X
ARCES		X	X	X	X	X
Secondary Outcomes						
Mental Health						
PCL		X			X	X
DASS-21		X			X	X
NSI		X			X	X
Functional/Vocational						
WHODAS-2.0		X			X	X
SWLS		X			X	X
Treatment/Activities						
Survey						
BESI		X			X	X
Average hours worked		X			X	X
Cognitive Outcome						
FrSBe		X			X	X
Feasibility & Program Satisfaction						
	X	X	X	X	X	X

### Analytic Plan & Power Analysis

\* Analytic Plan & Power calculations may include references to the full study sample, including Phase 2 recruitment at site 2 (Houston).

\*\*The February 2023 project modification/1-year extension requested funds to complete Cohort 19 (ongoing at the time of the project modification request) and enroll one additional cohort (Cohort 20) to ensure sufficient power for Aim 1 (Hypotheses 1A, 1B) and Aim 2, and to support final data analysis and manuscript submission in the last 6 months of the 1-year cost extension (October 2023 – March 2024). Of note, the study's Aims, listed below, remain unchanged with the project modification. The only changes involve an increase in our targeted enrollment number, to ensure sufficient power, as enrollment and measures completion rates to date are slightly under our original goals.

Data Management. Data entered in the database will be verified and quality assurance procedures will be followed; Human Subjects (*Accuracy/ Integrity of Data*); Data management plan (“09\_VA\_DMAP”).

For continuous variables, the mean, median, standard deviation, minimum, maximum, interquartile range, and sample size for each intervention group will be reported at each time point. For categorical variables the frequency distribution will be reported for each treatment group.

Baseline Comparability. While no substantial differences between intervention groups are anticipated given randomization, we will use summary statistics, graphical techniques such as boxplots, and univariate analyses to compare baseline characteristics of groups. Pre-intervention values will be compared between

STEP-Home and PCGT groups using t-tests and chi-squared tests, as appropriate, to determine if the groups are balanced with respect to baseline characteristics. This comparison will allow us to identify potential confounders and moderators to be included in multivariate analyses. Clinical covariates include: age; education; diagnosis of TBI history; PTSD, mood disorder, anxiety, substance use, chronic pain, sleep quality.

Statistical Methods by Research Aims. The primary analysis for each aim will use an intent-to-treat (ITT) approach (i.e., all randomized subjects will be used in the analysis). ITT is optimal since it provides the least biased estimate of the treatment effect and the randomization balances STEP-Home and PCGT groups on known and unknown baseline confounders. This approach is appropriate for the proposed study given an anticipated low attrition rate of ~17% (based on attrition rates observed in our SPiRE study and Mt. Sinai's STEP RCT). We will implement quality assurance procedures to minimize protocol deviations and ensure correct treatment assignment according to the randomization. As a sensitivity analysis, we will conduct a per-protocol analysis in the subset of participants who complete an adequate amount of treatment ( $\geq 80\%$  of weekly sessions). We will assess the assumptions of homogeneity of variance and normality of residuals for each regression model and apply an appropriate transformation of the outcome if needed. We will address missing data, under the assumption of missing at random, using multiple imputation. Any subject characteristics associated with both the treatment group and primary outcome measure will be adjusted for in the final statistical model as specified in each aim.

**Aim 1. Examine treatment effects of STEP-Home on primary outcomes relative to PCGT:**

***Hypothesis 1A. Participants randomized into the STEP-Home intervention will show improvement on reintegration, readjustment, and anger post-intervention (expressed by lower scores; less difficulty).***

Military to Civilian Questionnaire (M2CQ), Post-Deployment Readjustment Inventory (PDRI), and State-Trait Anger Expression Inventory (STAXI-2) scores post-intervention (T4)  $<$  baseline (T1)

Statistical Methods: Paired t-tests will evaluate the difference between pre- (T1) and post-scores (T4), with a separate analysis for each primary outcome.

***Hypothesis 1B. Participants randomized into STEP-Home will show greater improvement in primary outcomes as compared to PCGT.***

1B.1: Change scores baseline (T1) to post-intervention (T4) STEP-Home  $>$  PCGT

1B.2: Post-intervention (T4) primary outcome scores STEP-Home  $<$  PCGT

Statistical Methods: Mixed models (PROC MIXED in SAS) will evaluate pre-post differences, with a separate model for each primary outcome. The Satterwaite option will be used to account for the clustering of subjects within cohorts (identified in Section 6.2) and calculate degrees of freedom accounting for any missing data. Group (STEP-Home/PCGT) will be the between-subjects factor and time-point (T1/T4) will be the within-subjects factor. We hypothesize that there will be a significant interaction between group and time-point, with a larger improvement between pre- (T1) and post-scores (T4) in STEP-Home than PCGT. While we do not anticipate a significant interaction by cohort or site, we will evaluate the 4-way interaction and all 2-way and 3-way interactions for time-point, group, cohort, and site. The model will be rerun removing any non-significant interactions. Linear regression will be used to evaluate the difference in post-intervention (T4) by group. The final mixed and regression models for each outcome will adjust for any identified confounders.

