### **4. Work Proposed**

**(a) Study Objectives:** There are two major experimental objectives to this project: (1) To examine treatment effects of STEP-Home on primary outcomes relative to Present Centered Group Therapy (PCGT); (2) To examine maintenance of treatment effects on primary outcomes; and two exploratory aims: (1) To examine treatment effects on secondary outcomes targeted indirectly in the workshop; (2) To determine if acquisition of core skills or “key ingredients” mediates primary outcomes. In February 2023, we received approval for a 1-year cost extension to continue this study for one additional year; the study end date is now 3/31/24 instead of 3/31/23. Therefore, the objectives listed above will be accomplished across a 5-year timeline, instead of the original 4-year timeline.

**(b) Study Design (Phase 1):** We will conduct a randomized control trial (RCT) of STEP-Home at the VA Boston Healthcare System, Jamaica Plain campus and the Michael E. DeBakey Medical Center in Houston. With the 1-year study extension approved in February 2023, our funded aims have been updated to enroll 144 Veterans in Boston (original enrollment number was 112 in Boston) and 96 in Houston for a total of 240 participants. In order to achieve this, given drop out, we will recruit 300 Veterans overall, when accounting for participants at both sites.

[figure not shown]
Recruitment will be conducted in Boston (Years 1-5) and Houston (Years 3-5). Beginning in Year 3, Houston TRACTS/STEP-Home staff will assist in recruitment and referrals. The Houston site will assist with any clinical and/or safety concerns for Houston Veterans under the leadership of site PI, [name], a licensed psychiatrist with ample experience in this arena in coordination with Boston and study PI, [name]. All study procedures across both sites will be reviewed by our Data Safety Monitoring Board and reported to local IRBs at both sites.

Participants will be randomly assigned to receive one of the two group interventions: STEP-Home or PCGT, and each intervention will meet one time a week for 12 weeks. We will use statistical software to conduct cluster randomization to assign veterans to the intervention group. We do not plan to use matching or stratified

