randomization to balance the interventions on patient characteristics (e.g. age, prevalence of traumatic brain injury and psychiatric conditions, etc.) since we do not have any a priori reason to expect that such factors will significantly influence our primary outcomes. We will assess any patient characteristics as possible confounders in our analyses if they differ across groups (see Analytic Plan below). Given the group treatment modality for both conditions, it will be necessary to accrue participants for a cohort before randomization and treatment can begin. Each cohort will include a minimum of 8 and a maximum of 20 participants who will be randomized to either STEP-Home (n=4-10 Veterans per treatment group) or PCGT (n=4-10 Veterans per active control). The treatment group and active control group will be matched in size (n's equal at randomization) and populated based on recruitment success. The goal will be to recruit 16 Veterans and randomize to two groups of 8. However, if recruitment is slow, the smallest randomization pool allowed will be 8 (4 Veterans assigned to each group). If recruitment is ahead of pace, the largest randomization pool allowed will be 20 (10 Veterans assigned to each group).

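### The Hypothesis 1B mixed model writes no random therapy-group effect on change, and the one term that could carry it is removed when non-significant

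*Combined protocol and SAP*

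**What the plan says.** The statistical methods for Hypothesis 1B fit a mixed model to each primary outcome, with arm between subjects and T1/T4 within subjects. The arm-by-time interaction is the test of interest. On clustering the paragraph says "The Satterwaite option will be used to account for the clustering of subjects within cohorts" and points to a Section 6.2. It does not write out a random effect or say whether cohort is fixed or random.

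It then states that "we will evaluate the 4-way interaction and all 2-way and 3-way interactions" of time-point, group, cohort and site, followed by "The model will be rerun removing any non-significant interactions". No significance level or order of removal is given. Aim 2 and Exploratory Aim 1 reuse these models.

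Section 4(b), Study Design, defines the unit: "Each cohort will include a minimum of 8 and a maximum of 20 participants who will be randomized to either STEP-Home" or PCGT. On size: "The goal will be to recruit 16 Veterans and randomize to two groups of 8". The Power Analysis inflates the sample size for Hypothesis 1B using an ICC of 0.04 and arrives at 208.

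**The concern.** Both interventions are delivered in groups, so Veterans in the same therapy group may change together. A cohort is a pool containing both arms, so the therapy group is the cohort × arm cell and its effect on change is cohort × group × time. If the model has no random term at that level, the arm-by-time test uses the variation between individuals as its error, and the standard error is too small.

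The plan puts this term among the interactions to be screened. At an ICC of 0.04 the screen has little power, so the term would usually be removed. The clustering that the sample size paid for would then be missing from the analysis. At stake is the error rate of the main between-arm test on three primary outcomes.

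**Working it through.** **Inputs from the documents.** Power Analysis: d = 0.44, one-sided 0.05, 80% power, ICC 0.04, attrition 20%, total 208. Section 4(b): therapy groups of 8 as the goal, 240 enrolled. Analytic Plan, February 2023 note: cohorts run to Cohort 20.

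**Assumptions.** The ICC applies to change scores, the removal level is 0.05, data are balanced and complete, site is ignored, and only the cohort × group × time term is screened.

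**Layouts.**
- A: 20 cohorts, 240/20 = 12, so 6 per therapy group.
- B: as A with 20% loss, 6 × 0.80 = 4.8, taken as 5.
- C: the planning layout, 208/16 = 13 cohorts, 8 per therapy group.

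**1. Reproduce the 208.** A two-sample t-test with d = 0.44, one-sided 0.05 and 80% power needs 65 per arm, 130 in total. With cluster size 8 the inflation is 1 + (8 − 1) × 0.04 = 1.28. Then 130 × 1.28 / 0.80 = 208. With the whole cohort of 16 it is 130 × 1.60 / 0.80 = 260. Size 16 gives 208 only if attrition is left out (130 × 1.60), and the text says attrition is included. The figure therefore fits clustering at the therapy-group level.

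**2. Why a cohort term does not help.** In cohort j the difference between arm means is: treatment effect + (g₁ⱼ − g₂ⱼ) + individual error, where g is the therapy-group effect. Anything shared by the cohort cancels; the g terms do not. The variance of the estimated arm effect is 2(σ²_g + σ²_e/m)/J, for J cohorts and m per therapy group. The Satterthwaite option sets degrees of freedom; it adds no variance component.

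**3. How often the term is dropped.** P(drop) = P[F < F₀.₉₅ / (1 + mθ)], θ = 0.04/0.96, with J − 1 and 2J(m − 1) df. The factor 1 + mθ is 1.25 (A), 1.21 (B) and 1.33 (C), giving 82%, 85% and 81%.

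**4. Type I error (one-sided, nominal 5%, ICC 0.04).** A large-sample check for the model without the term is 1 − Φ(1.645/√(1 + (m − 1) × 0.04)). It gives 6.7% (A), 6.3% (B) and 7.3% (C). Simulation with no treatment effect (200,000 trials per cell) gives:

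| Rule | A | B | C |
|---|---|---|---|
| Screen; significant term kept as fixed | 7.0% | 6.6% | 7.7% |
| Screen; significant term kept as random | 6.0% | 5.8% | 6.4% |
| No screen; always kept as fixed | 7.0% | 6.7% | 7.8% |
| No screen; always kept as random | 5.0% | 5.0% | 5.1% |

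Repeat runs moved single entries by about 0.1 to 0.2 points, so the two screened rules are quoted as about 6.6 to 7.7% and 5.7 to 6.4%.

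**5. Other ICC values (screened, kept fixed / kept random).**
- ICC 0: no inflation under either rule.
- ICC 0.01: 5.5 to 5.7% / 5.1 to 5.3%.
- ICC 0.02: 5.9 to 6.4% / 5.5 to 5.8%.
- ICC 0.10: 9.2 to 11.4% / 6.4 to 6.7%. Here the term is dropped in only 51 to 61% of trials.

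**6. Cause.** Rows 1 and 3 of the table are almost equal. Screening adds nothing to the inflation beyond what a fixed interaction already has; only the always-random row is at 5%.

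**The case against.** The strongest reply is that the clustering sentence stands apart from the interaction screen and refers to a Section 6.2 that is not in the available text. The planners evidently had therapy-group clustering in mind, since 208 fits cluster size 8. If a random therapy-group-by-time term is in their model, or if cohort in that sentence means therapy group, then dropping a fixed interaction leaves the clustering in place. This stands in part: the documents do not prove that the clustering is ignored, and they never call the cohort interactions fixed. But Section 4(b) defines a cohort as the two-arm pool, and a group × cohort interaction exists only if cohorts contain both arms. On the text as written, the needed term is not specified.

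A reader might infer that the search for interactions is itself what inflates the error. The calculation does not support this, because always keeping the fixed interaction gives the same result.

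A reader might also infer that the four-way term cannot be estimated. It spans 20 × 2 × 2 = 80 cells for 240 people, an average of 3, and Houston recruits only from Year 3. The documents do not say how sites mix within cohorts, so sparse or empty cells are likely in early cohorts, but general inestimability is not shown. Dropping that term does not itself bias the arm-by-time estimate.

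Finally, the simulation is a simplification of the plan's full sequence of tests, and its size depends on the ICC scale. The Power Analysis does not say whether 0.04 refers to post-intervention or change scores.

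**Conclusion.** The concern holds as a gap in specification. The Hypothesis 1B model names no random therapy-group effect on change, and the only listed term that could carry it may be deleted on a weak test. Under the stated assumptions and the plan's own ICC, one-sided error rises from 5% to about 6.6 to 7.7% if a significant term is kept as fixed, and to 5.7 to 6.4% if it is kept as random. It is about 6% at ICC 0.02. Equivalently, the standard error should be about √1.16 = 1.08 to √1.28 = 1.13 times the unclustered one.

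This is modest inflation, conditional on a random-effects structure that the text does not show. It should be fixed before analysis, but it would be too strong to say that the primary test is invalid.

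**What to change.** Write the primary model for each outcome as group, time, group × time and cohort, with a random cohort × arm effect and its change over time. Keep the random terms whatever their p-values, with Satterthwaite degrees of freedom. Take the drop-and-rerun rule out of the primary model. Report cohort and site interactions, for example group × time × site, as separate checks that never alter it. If cohort was meant as therapy group in the clustering sentence, say so. The T4 linear regression in the same paragraph states no therapy-group term either and needs the same treatment.

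The cost is wording plus degrees of freedom. With 20 cohorts the arm contrast has about 19 (20 − 1, cohort fitted) to 38 (40 therapy groups − 2). The one-sided critical value rises from 1.645 to between 1.686 and 1.729, so the interval is slightly wider. Power survives: for 20 cohorts with 5 per therapy group, SE = √[2(0.04 + 0.96/5)/20] = 0.152 and 0.44/0.152 = 2.89, which on 19 df gives about 87%.
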